### **3.2 Study Population**

All patients registered and enrolled to the SMBG clinic in Klinik Kesihatan Senawang during the period of 1 January 2023 to 1 July 2023

### **3.3 Inclusion Criteria**

1. Established T2DM patients, already on insulin therapy regardless of the type of insulin or regime or duration of treatment
2. HbA1c at referral more than 8.5%
3. Already seen by diabetic educator or dietitian prior to referral
4. Completed a minimum of 3 follow-ups under the SMBG Clinic
5. Has HbA1c recorded at 6 months

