## Research Synopsis

Study title	Analogy As A Possible Effective Consultation Tool In Type II Diabetes Mellitus Patients on Insulin: A Retrospective Cohort Study
Objective	To determine the effectiveness of a novel consultation tool & method based on analogies in improving glycemic control among type 2 diabetes patients on insulin
Study Design	
This design will be a retrospective cohort study. We have clinical data of 107 T2DM patients registered in a newly established SMBG clinic in Klinik Kesihatan Senawang from 1 January 2023 to 1 July 2023. These clinic sessions are conducted once a week, and use a new structured consultation tool based on an analogy to explain and consult these patients. Patients are followed up every 2 months. Their HbA1c will be measured after 3 sessions of consultations (6 months). Patients who defaulted the follow up will be excluded.
 
We will prepare a medical record abstraction form and collect demographics and clinical data from the EMR. Demographic

[figure not shown]
	data included are patients' age and gender. Clinical data collected will be baseline HbA1c and FBS at first visit and third visit (after six months). Data will be analyzed to compare the following: (1) the percentage of patients achieving reduction of HbA1c and Fasting Blood Glucose (2) Average reduction of HbA1c and Fasting Blood Glucose
Study endpoints/outcomes	Reduction of HbA1c and Fasting Blood Glucose levels after six months, after a minimum of 3 SMBG clinic visits.
Study Population	All patients enrolled and registered at the SMBG clinic in Klinik Kesihatan Senawang from 1 January 2023 to 1 July 2023.
Inclusion/Exclusion Criteria	
Inclusion criteria
 
 
1. Established T2DM patients, already on insulin therapy regardless of the type of insulin or regime or duration of treatment
 
2. HbA1c at referral more than 8.5%
 
3. Already seen by diabetic educator or dietitian prior to referral
 
4. Completed a minimum of 3 follow-ups under the SMBG Clinic
 
5. Has repeated HbA1c recorded at 3 follow-ups
 
 
Exclusion Criteria
 
 
1. Pregnant, or found to be pregnant during follow up
 

Sample Size	106 Subjects (universal sampling)
Study Duration	15 March 2024 - 15 June 2024 (3 Months)

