## 1. Background and Significance

- 1.1. Diabetes prevalence in Malaysia has been steadily increasing. According to data from the National Health and Morbidity Survey (NHMS), conducted by the Ministry of Health Malaysia, the rate of diabetes among adults aged 18 and above rose from 8.4% in 2011 to a concerning 13.4% in 2019. This significant increase in diabetes rates is a matter of great concern that requires immediate attention. As diabetes progresses over time, oral hypoglycemic agents (OHAs) may become less effective. Therefore, insulin therapy becomes necessary to maintain proper blood sugar control. The use of insulin therapy among Type 2 diabetes patients in Malaysia has been increasing to align with recent local and international diabetes guidelines.
- 1.2. Despite the growing use of insulin therapy, a significant number of patients fail to achieve long-term blood sugar control. Audits revealed that only a small percentage of patients on insulin therapy achieve the desired HbA1c level below 6.5%. Approximately 10-15% of patients successfully reach the recommended blood sugar targets. Research also indicates that insulin is often prescribed with less intensive regimens and insufficient dosage optimization.
- 1.3. Multiple obstacles hinder optimal blood sugar control, including poor medication adherence, hypoglycemia, inadequate insulin dosage adjustments, reluctance to escalate insulin regimens (especially those requiring more frequent injections), and the underutilization of mealtime and basal insulin within basal-bolus regimens. One of the most under-addressed reasons is the patient's insight and understanding of diabetes itself. Multiple studies have shown that knowledge has direct correlation with improved glycaemic control. Healthcare workers, particularly physicians are the ones who will provide information regarding diabetes. While there are local Clinical Practice Guidelines for T2DM, there is currently no standardized guide on how to actually communicate and disseminate this information.

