## **2. Objective**

To determine the effectiveness of a novel consultation tool based on analogies in improving glycemic control among type 2 diabetes patients on insulin with HbA1c and FBS as primary outcomes.

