## **3. Methodology**

### **3.1 Study Design**

This design will be a retrospective cohort study. Clinical data of 107 T2DM patients enrolled in the SMBG clinic in Klinik Kesihatan Senawang from 1 January 2023 to 1 July 2023 (6 months) will be extracted from the electrical medical record (EMR). Patients who defaulted the follow up intervals will be excluded, as well as those without a repeated HbA1c. We will prepare a medical record abstraction form and collect demographics and clinical data. Demographic data included are patients' age and gender.

Clinical data collected will be baseline HbA1c and FBS at first visit and fourth visit (after six months). Data will be analyzed to compare the following: (1) the percentage of patients achieving reduction of HbA1c and FBS from baseline (2) Average reduction of HbA1c and FBS from baseline.

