### **3.9 Statistical Analysis Plan**

The data analysis will be done using the SPSS version 29. Descriptive data will be expressed as mean  $\pm$  standard deviation (SD) unless otherwise stated. Paired T-Test will be used for analysis of normally distributed variables. Wilcoxon signed-rank test will be used for non-normally distributed data. A value of  $P < 0.05$  is considered statistically significant.

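### Entry is selected on referral HbA1c above 8.5% and the source of the first-visit baseline is not stated; if it is the qualifying value and HbA1c is otherwise stable, a fall is expected with no effect

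*Combined protocol and SAP*

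**What the plan says.** Inclusion criterion 2 (section 3.3, repeated in the Research Synopsis) requires "HbA1c at referral more than 8.5" per cent. Section 2 sets out to determine the effectiveness of the tool "with HbA1c and FBS as primary outcomes".

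Section 3.1 defines the data as follows: "Clinical data collected will be baseline HbA1c and FBS at first visit and fourth visit (after six months"). The Synopsis has "baseline HbA1c and FBS at first visit and third visit (after six months"). The third-visit/fourth-visit discrepancy is a separate matter; both versions place the baseline at the first visit. Neither gives the date, window or source of that value, and the referral HbA1c is not listed among the data to abstract.

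The two planned summaries are "the percentage of patients achieving reduction of HbA1c and FBS from baseline" and the average reduction. The inference in section 3.9 is "Paired T-Test will be used for analysis of normally distributed variables", with the Wilcoxon signed-rank test otherwise and significance at P<0.05. There is no comparator, and regression to the mean is not mentioned.

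**The concern.** HbA1c is both the variable that selects patients and a primary outcome. A paired test takes zero as the change expected with no effect. For patients chosen because one reading exceeded a cut-off, zero is the wrong reference if that same reading is also the baseline. Some of them were above 8.5% partly by chance or on a temporary high, and their next reading will on average be lower whatever the consultation contained.

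Both planned summaries would then lean towards the tool, and P<0.05 would not separate an effect from selection. FBS was not the selection variable, so it is affected only indirectly, through its correlation with HbA1c.

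The question is therefore whether the plan says which value is the baseline, and how much depends on the answer.

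**Working it through.** **Where the baseline comes from.** The plan uses different labels: at referral for eligibility, at first visit for baseline. The first-visit content in section 1.5 and Figure 2 is history, analogy and insulin education, with no HbA1c sample mentioned. No FBS sample is mentioned there either, yet first-visit FBS is to be abstracted, so that silence proves little. Describing the later HbA1c as repeated fits either reading. Figure 1, the clinic flow chart, could not be read in the copy available here.

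**Inputs from the documents.** Threshold 8.5% (3.3). N=106 (3.6; section 3.1 says 107). Alpha 0.05 (3.9), taken as two-sided, so the nominal chance of a significant fall is 2.5%. N=106 is a headcount with no power calculation, so there is no planned figure to reproduce. It is also an upper case, because "Patients who defaulted the follow up intervals will be excluded, as well as those without a repeated HbA1c".

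**Assumed inputs.** The documents give none of these: HbA1c normal in the source population, mean μ 8.5 to 10, SD 1.8, six-month correlation ρ 0.6 to 0.95, no effect.

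**Step 1: baseline = qualifying value, no drift.** Let z = (8.5 − μ)/SD and λ = φ(z)/(1 − Φ(z)).

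- Expected fall = (1 − ρ) × SD × λ.
- SD of change s = SD × √[(1 − ρ)²v + 1 − ρ²], with v = 1 + zλ − λ².
- Chance of a significant fall: upper tail of the noncentral t with noncentrality (fall/s) × √N.

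For μ=9.0 and ρ=0.7:

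- z = −0.278, λ = 0.630, SD × λ = 1.134, so the fall is 0.3 × 1.134 = 0.340.
- v = 0.428, so s = 1.8 × √(0.09 × 0.428 + 0.51) = 1.333.
- Noncentrality = 0.340/1.333 × √106 = 2.63, which gives 74%.

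| μ | ρ | Fall (points) | Patients with a reduction | N=106 | N=80 | N=50 |
|---|---|---|---|---|---|---|
| 8.5 | 0.6 | 0.57 | 65% | 97% | 92% | 75% |
| 9.0 | 0.7 | 0.34 | 60% | 74% | 62% | 42% |
| 9.0 | 0.9 | 0.11 | 56% | 31% | 24% | 17% |
| 10 | 0.95 | 0.03 | 52% | 8% | 7% | 6% |

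The percentages with a reduction were simulated. Simulated paired t-tests (8,000 runs) agree with the first, second and fourth rows to within about 1.5 percentage points. The Wilcoxon test at N=106 gives 97%, 72% and 9% for those three rows. With SD 1.4 or 2.2, the 74% becomes 67% or 78%.

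**Step 2: upward drift.** Section 1.1 notes "As diabetes progresses over time, oral hypoglycemic agents (OHAs) may become less effective", so some worsening without the tool is plausible. Drift subtracts from the fall. At μ=9.0, ρ=0.7, N=106:

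- +0.1 leaves 0.340 − 0.1 = 0.240 (45%).
- +0.2 leaves 0.140 (19%).
- +0.3 leaves 0.040 (5%).

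At μ=10, ρ=0.95, +0.05 turns the fall into a rise (0.032 − 0.05 = −0.018) and the chance drops to 1%.

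**Step 3: a separate first-visit value.** Assume it is taken 2 months after referral, so follow-up is 8 months after referral. The expected fall is [corr(referral, first visit) − corr(referral, follow-up)] × SD × λ. For μ=9.0, first-visit-to-follow-up correlation 0.7, N=106:

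- Equal correlations: (0.7 − 0.7) × 1.134 = 0; significant fall about 2%.
- Part noise, part decay, corr(t) = 0.35 + 0.5 × 0.7^(t/6): (0.794 − 0.661) × 1.134 = 0.15; about 20%.
- Exponential decay, 0.7^(t/6): (0.888 − 0.622) × 1.134 = 0.30; about 63%. This is an extreme case with no lasting differences between patients.

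**The case against.** The strongest reply is that the plan labels the baseline as a first-visit value and eligibility as a referral value, so on its face the two differ. If so, and if correlation does not decay much between visits, the selection problem largely disappears and what remains is mainly the general limit of a study without a comparator. This stands as a possibility, and Figure 1 might confirm it.

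It is also fair that the size is barely constrained. Every input beyond 8.5% and 106 is assumed, no cell of the table has a better claim than another, and modest upward drift can cancel the bias or reverse it.

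A reader might go further and infer that the qualifying value is the baseline, that any reported fall is an artefact, or that 74% is this study's false-positive rate. The documents support none of these. They leave the baseline's source open, and they give no mean, SD, correlation or drift from which a rate for this clinic could be computed.

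What the reply does not remove is that the plan selects on a primary outcome, tests change in it against zero, and does not ask for the information that would show which case applies.

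**Conclusion.** The concern holds in conditional form. If the qualifying HbA1c serves as baseline and HbA1c is otherwise stable, a fall is expected with no effect. Only the direction is firm; the ranges above show what could happen under the stated assumptions and do not estimate what will happen in this clinic.

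A separate first-visit baseline helps, but it protects fully only if correlation is equal at all lags. The limit on interpretation is therefore needed whichever baseline was used.

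This should be fixed before analysis. It affects which value enters the test and what a significant result may be said to show, so it is more than a missing detail.

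**What to change.** 1. **Section 3.1:** abstract the referral HbA1c, which must be looked up anyway to apply criterion 2, and record the date and source of both the referral and the baseline values.
2. **Section 3.9:** use a separate, non-qualifying first-visit HbA1c as baseline where one exists, report how many patients have only the qualifying value, and repeat the paired analysis restricted to patients with a separate baseline. Without the restricted analysis, the main test would mix the two kinds of baseline.
3. **Section 3.9:** state that P<0.05 shows a before-after change in patients who completed the clinic pathway, may include regression to the mean, and will not by itself be read as effectiveness of the analogy tool.

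A sensitivity comparison of six-month HbA1c with an earlier EMR value is optional. It is weak if that value also exceeded 8.5%: at μ=9.0, ρ=0.7, N=106, a significant fall with no effect still occurs in about 43% (equal correlations) to 68% (decaying).

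**Cost.** No patient contact, but some extra abstraction. Section 3.13 says the data were anonymized before extraction, so a second extraction may be needed; section 3.14 describes a study identification number, but not whether a key to the records is kept. The restricted analysis will have a smaller N, and the headline claim becomes more modest.

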### **3.4 Exclusion Criteria**

1. Pregnant or found to be pregnant during follow-up

### **3.5 Withdrawal Criteria**

Not applicable

## 3.6 Sample Size

106 patients. This study will use a universal sampling method. 106 patients were enrolled in the SMBG Clinic of Klinik Kesihatan Senawang from 1 January 2023 to 1 July 2023.

### 3.7 Study Duration and Timeline

- Start date: 20 March 2024
- End date: 20 September 2024
- Stage 1, review of medical records - 2 months
- Stage 2, data collection and data analysis - 2 months
- Stage 3, presentation and publication - 2 months

## Gantt Chart

### **3.8 Study Visits and Procedures**

Not applicable

### **3.9 Statistical Analysis Plan**

The data analysis will be done using the SPSS version 29. Descriptive data will be expressed as mean  $\pm$  standard deviation (SD) unless otherwise stated. Paired T-Test will be used for analysis of normally distributed variables. Wilcoxon signed-rank test will be used for non-normally distributed data. A value of  $P < 0.05$  is considered statistically significant.

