- 1.4. In clinical practice, analogies are recognized as valuable tools for facilitating communication while enhancing doctor-patient interactions, particularly in elucidating complex medical concepts. It is widely used in oncology to communicate with patients about their current condition. When presented in vignette form, analogies have demonstrated a potential for increasing objective comprehension among patients. They offer a means for simplifying intricate medical concepts, thus improving patient comprehension and engagement, ultimately leading to better health outcomes. This represents a promising approach to enhancing doctor-patient communication in a very complex disease like T2DM. However, the effectiveness of analogies may vary depending on the complexity of the medical issue and the numeracy level of the individual, highlighting the importance of tailoring analogies to suit the needs and cultural context of the patient.
- 1.5. Hence, we developed a consultation tool based on the “Garbage, lorry, factory” analogy. In this analogy, the garbage represents glucose, the lorry represents insulin, and the factory represents the muscle. We tested this method through a

specialized clinic in Klinik Kesihatan Senawang, Negeri Sembilan from January 2023, where patients are referred to a 2-monthly consultation with primary care doctors. On the very first visit, patients are clerked to provide baseline background information. Then, they will be presented with the “Garbage and Lorry” analogy, assisted by a visual tool (Appendix 1), to explain the pathophysiology of T2DM. The presentation includes detailed lifestyle modification advice like diet, exercise, sleep. It ends with an explanation of the pharmacology of the common T2DM drugs and insulin, all guided by the same analogy. At the end of the consultation, patients would be given an insulin intensification protocol built based on Malaysia’s local guidelines that they would have to follow, and was given a follow up after 2 months, with a 4-point SMBG chart to be monitored a week before. The follow up would be reviewing the SMBG, and optimizing their insulin regime based on the blood glucose profile. Once their SMBG is optimized, their HbA1c is repeated. Figure 1 shows a flowchart of how the SMBG clinic runs.

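### Section 3.9 tests two primary outcomes for change from baseline with no interval, no reporting rule for the percentages and no success rule, although a significant fall can occur without any effect of the tool

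*Combined protocol and SAP*

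**What the plan says.** Section 2 asks whether the analogy tool improves glycaemic control, "with HbA1c and FBS as primary outcomes". Section 3.1 lists two comparisons: "the percentage of patients achieving reduction of HbA1c and FBS from baseline" and "Average reduction of HbA1c and FBS from baseline". The synopsis lists the same two.

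Section 3.9 names SPSS 29, mean and SD, the rule "Paired T-Test will be used for analysis of normally distributed variables. Wilcoxon signed-rank test will be used for non-normally distributed data", and a threshold of P < 0.05. It mentions no confidence interval. It gives no method, cut-off or denominator for the percentages, and no hierarchy, either/both rule or adjustment for the two primaries. No other section supplies these.

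Four other statements bear on how a change from baseline can be read:

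- Section 3.3 requires "HbA1c at referral more than 8.5"%.
- Section 1.5 says that at the end of the first consultation "patients would be given an insulin intensification protocol". Figure 2 lists insulin titration teaching in the same visit, and follow-up consists of SMBG review and insulin adjustment.
- Section 1.5 also says "Once their SMBG is optimized, their HbA1c is repeated".
- Section 3.1 says "Patients who defaulted the follow up intervals will be excluded, as well as those without a repeated HbA1c". Section 3.3 likewise requires at least three follow-ups and a six-month HbA1c.

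Section 3.6 gives 106 patients, a count of everyone enrolled (section 3.1 says 107). There is no power or precision calculation.

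**The concern.** The average reduction is the natural main result, yet the plan commits only to a P value and to means with SDs. Visit-level SDs do not give the precision of a paired change, which depends on the within-patient correlation. If Wilcoxon is used, its P value does not test the mean, although the endpoint is an average.

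The percentage achieving reduction, read literally, counts any fall. With no comparator, readers will tend to judge it against 50%, but 50% is not a fixed no-effect value for HbA1c in patients selected for being high.

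Two primaries at P < 0.05 with no rule leave it open, once results are known, whether one success is enough.

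The largest consequence is interpretation. The objective is worded as the effectiveness of the tool, and the planned test asks only whether the change differs from zero. Followed as written, the plan could credit the tool with a fall that selection, insulin intensification or the restriction to completers produced.

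**Working it through.** There is no plan figure to reproduce: 106 is a census count.

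**Inputs.** From the documents: two primaries, threshold 0.05, selection above 8.5%, and at most 106 analysed (107 would change nothing material). Assumed, because the documents give no values: HbA1c mean 9.0 and SD 1.8 in the source population (wider ranges in step 3), correlations as stated, and 80 or 60 as possible analysed numbers after exclusions.

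**1. Precision of the mean change.** Half-width = t(0.975, n−1) × SD_d / √n, with SD_d = 1.8 × √(2(1−r)). This gives SD_d = 1.80 at r = 0.5 and 1.14 at r = 0.8.

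| n | r = 0.5 | r = 0.8 |
|---|---|---|
| 106 | 1.983 × 1.80 / 10.296 = 0.35 | 0.22 |
| 80 | 1.990 × 1.80 / 8.944 = 0.40 | 0.25 |
| 60 | 2.001 × 1.80 / 7.746 = 0.46 | 0.29 |

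The visit SDs are the same in both columns, so they cannot tell a reader which half-width applies.

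**2. Change with no effect, first-visit baseline.** With values recorded to 0.1, above 8.5 means at least 8.55 before rounding. Then z = (8.55 − 9.0)/1.8 = −0.25, and patients selected lie on average φ(0.25)/Φ(0.25) = 0.3867/0.5987 = 0.646 SD above the source mean at referral. The expected change from first visit to follow-up is −(r_referral,first − r_referral,follow-up) × 1.8 × 0.646 = −1.163 × the difference in correlations.

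- Correlations 0.90 (referral–first), 0.70 (first–follow-up), 0.63 (referral–follow-up): change −1.163 × 0.27 = −0.314. SD_d = 1.8 × √0.6 = 1.394. At n = 106, 0.314 × 10.296/1.394 = 2.32, and the chance of significance is about Φ(2.32 − 1.98) = 0.63.
- Correlations 0.90, 0.75, 0.70: change −1.163 × 0.20 = −0.233. SD_d = 1.8 × √0.5 = 1.273. At n = 80, 0.233 × 8.944/1.273 = 1.64, and the chance is about Φ(1.64 − 1.99) = 0.36.
- All correlations equal: the difference is zero, so the expected change is zero.

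Simulation, which also reflects the slightly narrower spread after selection, gives about 0.38 to 0.65 over four decaying sets and n = 80 to 106 (the ends move by 0.01 to 0.02 between runs), and about 0.05 with equal correlations. If baseline were the referral value itself, the shift would be (1 − r) × 1.163, or 0.35 at r = 0.7.

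The 95% CI from the paired t-test excludes zero in exactly the studies where that test is significant, so it carries the same bias.

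**3. Share with any fall in HbA1c, no effect.** Simulated for source means 8.5 to 10.0 and SDs 1.5 to 2.1:

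| Baseline | Correlations | Share falling |
|---|---|---|
| Referral value | equal, 0.6 to 0.8 | 52% to 64% |
| Separate first-visit test | equal, 0.6 to 0.8 | 48% to 49% |
| Separate first-visit test | decaying with time | 51% to 62% |

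Exact 95% CIs for a share near 60%: 50.4% to 69.7% (64/106), 48.4% to 70.8% (48/80), 46.5% to 72.4% (36/60).

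**4. Two primaries, each test assumed to hold 5%.** At least one false positive: 1 − 0.95² = 0.0975 if independent, 0.0907 at correlation 0.5, 0.0835 at 0.7 (bivariate normal). Both false positive: 0.0025, 0.0093 and 0.0165. If only one outcome is truly null, a both-must-succeed rule still cannot exceed 0.05.

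**The case against.** The strongest reply is that the plan is brief rather than wrong. Both named tests are paired, and the paired t-test suits an average reduction. SPSS prints an interval with it. A percentage in a single-group study is naturally descriptive, and section 3.1 places baseline at the first visit, which may already be a separate test. Much of this stands, and it rules out several stronger readings that a reader might infer:

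- **That 3.9 tests the wrong quantity.** It refers to the normality of variables without saying which. It is silent on within-patient differences; it does not reject them.
- **That Wilcoxon would mislead here.** That depends on the shape of the differences, on which the documents give nothing. With roughly normal differences the two tests seldom disagree.
- **That two primaries inflate the error.** They do so only if either one is allowed to carry the conclusion. The defect is the missing rule.
- **That a share above 50% can never indicate benefit.** The highest no-effect share in any setting examined is 64%. A share of 80% to 90% would lie beyond what selection alone gives in these models, though it still could not be credited to the tool.
- **That the planned test must give a spurious result.** With a separate first-visit baseline and equal correlations it keeps about 5%. The inflated rates need correlation that decays with time, or the referral value used as baseline.

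What remains is that printed output is not a commitment to report, and that neither the descriptive status of the percentages nor the source of baseline HbA1c is stated. Nothing in 3.9 limits the conclusion to what an uncontrolled change can support.

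**Conclusion.** The point holds and should be corrected. The three omissions (interval, percentage reporting, success rule) can be checked directly in sections 2, 3.1 and 3.9. Their more serious consequence is that a test against zero can be significant with no effect of the tool: from about 0.05 to about 0.65 of studies for HbA1c, depending on an unknown correlation pattern. These rates cover selection only; insulin intensification, HbA1c repeated after SMBG is optimised, and the restriction to completers come on top and are not quantified. The success-rule gap is smaller: about 8% to 10% against 5%, and only if either outcome suffices.

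The means, SDs and correlations are assumptions, so the figures show a plausible size and do not predict this study's result. The selection argument is made for HbA1c only, since patients are not selected on FBS. Adding an interval improves reporting but does not repair attribution.

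**What to change.** In section 3.9:

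1. Make the mean within-patient change with a 95% CI (paired t) the main estimate, and use Wilcoxon on the differences as a sensitivity analysis.
2. Name mean HbA1c change as the single primary, with FBS and the percentages secondary; or keep both primaries and state that both must be significant. Section 3.13 describes the record review in the past tense, so if results have been seen, label this choice post hoc.
3. Report the percentages descriptively, separately for HbA1c and FBS, with exact 95% CIs on the number analysed. State that a share above 50% is not by itself evidence of benefit.
4. Record for each patient whether baseline HbA1c is the referral value or a separate first-visit test, and report the counts.
5. Limit the conclusion to change observed under the whole clinic package. State that it cannot be attributed to the analogy tool, because of regression to the mean, concurrent insulin intensification and SMBG review, HbA1c being repeated once SMBG is optimised, and the restriction to completers.

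Items 1, 2, 3 and 5 are wording only; item 4 needs one field in the abstraction form. No extra patients or visits are needed. The cost is that, under the single-primary option, FBS and the percentages lose primary status, and the conclusion is narrower.
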